#### **3.4.1.5 Others**

##### **Baseline value**

For both efficacy and safety analyses the baseline value for all variables is defined as the last value obtained during screening period on or prior to the date of randomization.

##### **Geographic Region**

Geographic regions are defined as follows:

- Asia (China, Japan, Taiwan, Vietnam, India, Malaysia, Thailand)
- Europe (Austria, Bulgaria, Czech Republic, Germany, Hungary, Italy, Poland, Russia, Slovakia, Spain, Ukraine, UK, Turkey)

- North America (Canada, US)
- South America (Argentina, Brazil, Mexico, Peru)

The determination of the region will be based on the country recorded in interactive voice/web response system (IxRS) as a stratification factor.

### **Incomplete dates**

All efforts should be made to obtain complete dates of clinical assessments and events. For analyses requiring complete dates, partially missing dates will be imputed based on available corroborating information. Appendix 1 presents the dates that will be imputed and the associated rules.

### **Study day**

Study day related to event day or censoring day is derived using following formula: (event or censoring date – randomization date) + 1.

#### **3.4.2 Visit Window**

No visit windowing be applied.

#### **3.4.3 Handling of Unscheduled Visits**

Data obtained on unscheduled visits (e.g., safety laboratory evaluations) will be excluded from any analyses and presentations that are done for each visit separately. It will, however, be included in analyses of extreme values observed during a particular period of time, such as tabulations of high/low/out-of-range test results observed while a subject was on treatment. Data obtained on unscheduled visits will also be listed.

#### **3.4.4 Handling of Protocol Deviations in Study Analysis**

The section covers the list of potential Important Protocol Deviations (IPDs) that might potentially impact the results of the analyses and/or are a serious breach of Good Clinical Practice (GCP).

The IPDs will be categorized as follows:

1. Written informed consent not obtained prior to mandatory study specific procedures, sampling and analyses.
2. Received alternative protocol specific therapy than that which they were randomised.
3. Developed discontinuation of study intervention criteria during the study, but remained on the study intervention.
4. Site procedure for unblinding of the subject is not complaint with the CSP.
5. Received prohibited/excluded concomitant medication.

As the main efficacy analyses for the study follow the intention-to-treat principle, presence of protocol deviations for a subject will not imply exclusion of the subject, or any data obtained from the subject, from these analyses. However, supplementary analyses aimed at e.g., evaluating potential efficacy for subjects who remain on the assigned study treatment regimen might be conducted. As such analyses are per protocol in nature, they would exclude data obtained following a protocol deviation, see Section 4.2.

## 4 STATISTICAL ANALYSIS

This section provides information on definitions, derivation and analysis/data presentation per domain (study population, efficacy, safety).

### 4.1 Study Population

This section covers the presentation of subject recruitment, disposition, analysis sets, protocol deviations, demographics, baseline characteristics, medical history, prior and concomitant medication, exposure and study drug compliance. Data will be summarised by treatment arm and overall using FAS except for disposition and analysis sets overview.

#### 4.1.1 Subject Disposition and recruitment

##### 4.1.1.1 Definitions and Derivations

###### **Complete follow-up of the primary endpoint**

Subject having experienced the primary endpoint event, or the subject reaching SED is defined as having completed the follow-up for primary endpoint.

###### **Study completers**

Randomised subjects who stayed in the study until the SED irrespective whether they discontinued IP or had any event will be considered as study completers.

**Vital Status** of subjects at the end of the study will be recorded, if available, as dead or alive in the eCRF, along with the relevant dates. Vital status of the subjects that are lost to follow up (LTFU) will be recorded as 'unknown'.

##### 4.1.1.2 Presentation

###### **Disposition**

The presentation of patient disposition will include information on enrolment, randomization, receiving at least one dose of IP, completing the treatment and completing the study. It will summarise whether a subject did or did not experience these milestones and, if not, the reason. The presentation will also include the number of subjects with

complete follow-up of the primary endpoint and vital status of subjects at the end of the study (dead, alive or unknown).

The tabulation will include an overview of the number and percentage of subjects experiencing a particular disposition event, per treatment arm and in total, with number of randomized subjects in the respective treatment group, and in total, used as the denominator for the percentage calculation.

Number of subjects enrolled, but not randomized, as well as number of subjects with a certain reason for not being randomized, will only be displayed for all subjects combined, with no percentage calculated.

### **Disposition due to Country/Global Situation**

The number, and percentage, of subjects discontinuing treatment and discontinuing study due to Country/Global Situation (e.g. COVID-19), will be presented separately.

### **Randomised Subjects**

Randomized subjects by region, country and site will be presented in terms of number and percentage of patients randomized at a particular location, by treatment arm and in total.

#### **4.1.2 Analysis Sets**

##### **4.1.2.1 Definitions and Derivations**

Please refer to Section 3.2 for definitions of analysis sets. Note that only one reason for not being included in SS, while being included in FAS, is possible, namely failing to receive study intervention.

##### **4.1.2.2 Presentation**

An overview of the number of subjects included in, and, for SS, excluded from, the respective analysis set will be provided. The reasons for not being randomized, and, consequently, not being included in FAS or SS, will not be included in this presentation.

#### **4.1.3 Protocol Deviations**

##### **4.1.3.1 Definitions and Derivations**

All protocol deviations, regardless of the method of identification (e.g. manual vs programmatic), will be stored in the Veeva Clinical Vault (VCV) system, from which the final protocol deviation data set will be extracted and included as part of the data base. This data set will be the basis for the summaries and listings of protocol deviations.

##### **4.1.3.2 Presentation**

The number of subjects with any IPD, as well as the number of subjects experiencing an IPD in a particular category, will be summarized descriptively as categorical variables, as

described in Section 3.3. The presentation will also include the corresponding information specifically on the occurrence of Country/Global Situation related protocol deviations.

#### **4.1.4 Demographics**

##### **4.1.4.1 Definitions and Derivations**

Demographic data is recorded in the eCRF at the Screening Visit. Demographic variables summarized as part of the description of the study population are as follows:

- Age (years) as a continuous variable, and categorically as:
  - $\geq 18$  to 50, 51 to 64, 65 to 84 and  $\geq 85$  years
  - $< 65$ , 65 to 74, and  $\geq 75$  years
  - $< 65$  and  $\geq 65$  years
- Sex (Male, Female)
- Race (White, Black or African American, Asian, American Indian or Alaska Native, Native Hawaiian or other Pacific Islander, Other)
- Ethnicity (Hispanic or Latino, Not Hispanic or Latino)
- Geographic region and country as defined in Section 3.4.1.5)

##### **4.1.4.2 Presentation**

The demographic attributes as described above will be summarized descriptively as described in Section 3.3.

#### **4.1.5 Baseline and Disease Background Characteristics**

##### **4.1.5.1 Definitions and Derivations**

Baseline characteristics summarized as part of the description of the study population are as follows: height (cm), pre- and post-dialysis weight (kg) and body mass index (BMI) ( $\text{kg}/\text{m}^2$ ), continuous and categorical ( $30 < \geq 30$ ).

**The BMI ( $\text{kg}/\text{m}^2$ )**, defined as post-dialysis weight (kg) / (height (m)), will be derived for each subject.

Disease related background characteristics will include pulse (BPM), blood pressure (BP), S-K (mmol/L), continuous and categorical ( $< 5.5$ ,  $5.5-6.5$ ,  $> 6.5$ ) and inter-dialytic weight gain (IDWG).

**Interdialytic weight gain (IDWG)** will be calculated as the difference between current pre-dialysis weight and the previous post-dialysis weight (measured at preceding dialysis session prior to the visit) in kilograms. If current pre-dialysis weight or previous post-dialysis weight is missing, no interdialytic weight gain will be derived.

#### **4.1.5.2 Presentation**

The presentation of the baseline characteristic will follow the same rules as that for demographics.

#### **4.1.6 Disease Related Medical and Surgical History**

##### **4.1.6.1 Definitions and Derivations**

Disease related medical and surgical history will be coded using the version Medical Dictionary for Regulatory Activities (MedDRA) implemented in the study at the time of database lock.

##### **4.1.6.2 Presentation**

Presence of disease related medical or surgical history will be summarized descriptively by system organ class and preferred term, as a categorical variable, as described in Section 3.3. The MedDRA version used will be included in the relevant outputs as a footnote.

#### **4.1.7 Dialysis History**

##### **4.1.7.1 Definitions and derivations**

Dialysis history recorded on the eCRF at screening visit includes: (I) dialysis vintage (time since first dialysis in years); (II) type of access: AV fistula, AV graft, tunneled central venous catheter, other (specify).

##### **4.1.7.2 Presentation**

Time since first dialysis (years) will be summarized as a continuous variable and dialysis access type as a categorical variable, as described in Section 3.3.

#### **4.1.8 Prior and Concomitant Medications**

##### **4.1.8.1 Definitions and Derivations**

**Concomitant medication** is defined as a medication taken by the subject after the date of randomization, regardless of when it has been initiated.

Please see Appendix 1 for imputation rules for missing medication start and stop dates.

**Disallowed medication** is defined as a potassium binder that is taken post-randomization and is not identifiable as rescue therapy. Potassium binders are defined by the ATC terms listed in Appendix 3.

**Rescue** is defined as any potassium lowering treatment (e.g. a medication, an extra dialysis, a change in dialysate K concentration in the existing dialysis regimen) given in connection to an adverse event (AE) of hyperkalaemia requiring rescue.

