## 6.5 Concomitant Therapy

Any medication or vaccine (including over the counter or prescription medicines, vitamins, and/or herbal supplements) that the participant is receiving at the time of enrollment or receives during the study must be recorded along with:

- Reason for use
- Dates of administration including start and end dates
- Dosage information including dose and frequency

The Study Physician should be contacted if there are any questions regarding concomitant or prior therapy. The medications listed in [Table 5](#) are restricted during the study.

Restricted medications taken outside the conditions as specified in the “Usage” column, due to, eg, compelling medical reasons that necessitate such an action, will be considered as disallowed medications, the use of which constitutes a protocol deviation.

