**Table 5      Restricted Medications**

Restricted Medication/Class of Drug	Usage
Loop Diuretics: Bumex (bumetanide), Edecrin (ethacrynic acid), Lasix (furosemide), Demadex (torsemide)	Changes to loop diuretics (including adding a new changing the dose or discontinuation or switching of loop diuretics) during the study are discouraged. If changes in loop diuretics are clinically indicated this should be documented in the electronic case report form.
SZC (Lokelma)	Once the participant has been enrolled in the study, SZC cannot be used for rescue therapy.

CPS calcium polystyrene sulfonate; SPS Sodium polystyrene sulfonate.

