#### **6.5.2 Rescue Medicine**

Rescue therapy for controlling hyperkalemia is defined as any short-term (24 to 48 hours) therapeutic intervention during the study, that is considered necessary per the investigator's judgment and in accordance with local practice patterns to reduce S-K in the setting of an AE of severe hyperkalemia. See Hungary-specific text in [Appendix E](#).

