##### Rescue Therapy Permissible in Dialize-Outcomes Study

Specifically, rescue therapy applies only to short-term (24 to 48 hours) therapy to treat an AE of severe hyperkalemia as defined in the CSP. Note that rescue medications indicated for treatment of severe hyperkalemia encompass primarily rapid-acting IV or inhalable drugs that reduce serum potassium within a few hours (eg, insulin/glucose, beta adrenergic agonists, sodium bicarbonate); these drugs must take precedence over oral potassium binders in such acute setting given that oral binders have delayed onset of action and lack approval for life-threatening hyperkalemia. Potassium binders (other than SZC) should only be used for short periods of time (24 to 48 hours) to complement the action of rapid acting hyperkalemia rescue drugs. Potassium binders (other than SZC IP) are restricted medications and must not be used recurrently or for chronic treatment during the study.

The date and time of rescue medication administration, as well as the name and dosage regimen of the rescue medication, must be recorded. Rescue medication for hyperkalemia will not be provided as part of study medications ([Table 5](#)).

Rescue therapy includes, but is not limited to, any of the following:

- 1 Insulin/glucose, beta-adrenergic agonist, sodium bicarbonate, etc.
- 2 Other potassium binders: SPS (eg, Kayexalate, Resonium), CPS (eg, Resonium Calcium) and patiromer (Veltassa) ([Table 5](#)).

NOTE: All potassium binders other than SZC are considered restricted medications and can be used only for short-term rescue (24 to 48 hours). Once the participant has been enrolled in the study, SZC cannot be used for rescue therapy. SZC/placebo must be temporarily discontinued while rescue therapy is administered. [Table 5](#) lists medications restricted during the study.

- 3 Any additional dialysis or other forms of renal replacement treatments when used specifically for the treatment of severe hyperkalemia.
- 4 Any reduction in the Kd that is prescribed for the treatment of severe hyperkalemia during the study.

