## APPENDIX 3: ATC TERMS FOR POTASSIUM BINDERS

ATC CODE	RECNO	SEQNO1	SEQNO2	INGREDIENTS
V03AE	000677	01	001	SODIUM POLYSTYRENE SULFONATE
V03AE	003281	01	001	CALCIUM POLYSTYRENE SULFONATE
V03AE	075390	01	001	PATIROMER
V03AE	075390	02	001	PATIROMER CALCIUM
V03AE	075390	03	001	PATIROMER SORBITEX CALCIUM
V03AE	087714	01	001	SODIUM ZIRCONIUM CYCLOSILICATE

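### The SAP's rescue definition omits the protocol's limits on binder use, so prolonged binder courses and non-study SZC begun at a hyperkalaemia AE fall outside the disallowed-medication table

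*SAP*

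**What the plan says.** **SAP.** Section 4.1.8.1 puts non-study potassium binders into two bins. Disallowed medication "is defined as a potassium binder that is taken post-randomization and is not identifiable as rescue therapy". Rescue "is defined as any potassium lowering treatment" that is "given in connection to an adverse event (AE) of hyperkalaemia requiring rescue". Appendix 3 lists the binders by ATC term and includes "SODIUM ZIRCONIUM CYCLOSILICATE". Section 4.1.8.2 summarises all concomitant medications, disallowed medications and rescue treatments, each by ATC class and generic name.

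**Protocol.** Section 6.5 says that restricted medicines taken outside the Table 5 usage conditions "will be considered as disallowed medications, the use of which constitutes a protocol deviation". Table 5 allows SPS, CPS and patiromer only as rescue under Section 6.5.2. There, rescue "is defined as any short-term (24 to 48 hours) therapeutic intervention during the study". A note adds: "All potassium binders other than SZC are considered restricted medications and can be used only for short-term rescue (24 to 48 hours"). The same section forbids recurrent or chronic binder use, leaving aside the study product. For commercial SZC, Table 5 states that after enrolment "SZC cannot be used for rescue therapy".

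**The concern.** The two documents use the words rescue and disallowed differently. The protocol sets conditions, and whatever breaches them is disallowed. The SAP asks only whether the binder can be tied to a hyperkalaemia AE; if it can, the binder is rescue and cannot also be disallowed.

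This matters because the trial tests a contrast in potassium control, and ongoing non-study binder treatment narrows that contrast. Protocol Section 3 names rescue and other potassium-altering treatment as intercurrent events and handles them by treatment policy, so the main analysis ignores them. The descriptive tables are where a reader would look for how much ongoing binder treatment each arm received. A table that merges a two-day rescue with a course of several months does not answer that question, and a neutral result would be harder to interpret.

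**Working it through.** The plan states no figure on this point, so the check applies each document's rule to the same five patterns of use.

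| Use after randomization | Protocol 6.5, Table 5, 6.5.2 | SAP 4.1.8.1 with Appendix 3 | Agree? |
|---|---|---|---|
| SPS, CPS or patiromer, one course of 24 to 48 h at an AE of severe hyperkalaemia | Rescue | Rescue | Yes |
| Same agents, started at such an AE and continued beyond 48 h | Outside the conditions, so disallowed | Rescue | No |
| Repeated short courses, each at its own AE | Disallowed if this is recurrent use, a term the protocol does not define | Rescue each time | No, if recurrent |
| Non-study SZC started at such an AE | Disallowed | Rescue | No |
| Any listed binder with no linked hyperkalaemia AE | Disallowed | Disallowed | Yes |

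Every disagreement runs the same way: a use that the protocol disallows is rescue in the SAP. By construction it then leaves the disallowed table.

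**Where these uses would still appear**

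- *Concomitant medications (SAP 4.1.8.2, by arm under 4.1).* All users appear by drug. No duration is shown.
- *Rescue table (SAP 4.1.8.2).* The same users appear, mixed with short rescue.
- *Important protocol deviations (SAP 3.4.4 and 4.1.3).* Category 5, prohibited or excluded medication, could record them. It is not tied to the 24 to 48 h limit or the SZC bar, and its source is the deviation system, not the 4.1.8.1 derivation.
- *Drop-in analysis (SAP Table 1 and 4.2.1.6).* It censors at the start of non-protocolized SZC, for the primary endpoint only. Patiromer, SPS and CPS have no counterpart.

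So no planned output separates short rescue from prolonged use of a binder other than SZC. One participant could also be a category 5 deviation and yet be missing from the disallowed-medication table.

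**Size.** Let N be the number of binder courses in an arm that fall outside the protocol's conditions, and f the fraction linked to a hyperkalaemia AE. The disallowed table then captures N × (1 − f) courses and omits N × f, a share of f. The documents give neither N nor f. With f anywhere from 0 to 1, the omitted share runs from 0% to 100%.

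**Rescue endpoints.** Time to first rescue is fourth among the secondary endpoints in SAP Table 2, and Table 3 has a rescue count and a composite that includes rescue. The SAP does not say outright that the 4.1.8.1 definition feeds them. If it does, non-study SZC started at a hyperkalaemia AE would count as a rescue event.

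**The case against.** The strongest reply is that nothing is concealed. Every binder user appears by drug and arm in the concomitant-medication table, deviations have their own table, and non-protocolized SZC has a supplementary analysis. Protocol 7.1.1 also lists the need for chronic binders as a ground for stopping study intervention, and category 3 of the important deviations covers participants who met a stopping criterion but stayed on treatment. This largely stands. What is missing is the split by duration and agreement between tables, not the users themselves.

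A second reply is that rescue therapy is a protocol term, so the SAP may carry the protocol's limits silently, and that a course of many months is not plainly connected to one AE. That reading is possible. But the SAP writes its own definition, does not cite Protocol 6.5.2 there, and does not say when the link to an AE lapses. A programmer following the text has no duration rule to apply. No programming specification is available to settle it.

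Third, the protocol is not uniform. It counts a reduction in dialysate potassium as rescue within a 24 to 48 h definition, while Appendix E describes dialysate changes as longer-term management. That is a reason to reconcile the texts rather than simply copy one into the other.

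A reader might also infer that SAP Section 2 is wrong to declare no changes to the protocol's planned analyses. That is not supported: Protocol Section 9 plans no disallowed-medication table.

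**Conclusion.** The definitions conflict on the face of the documents. Followed as written, the SAP's disallowed-medication table leaves out AE-linked binder courses beyond 48 h, AE-linked recurrent use and AE-linked non-study SZC, and places them with rescue. The consequence is a misclassified by-arm summary and possible disagreement with the deviation tables. It is worth correcting, but it has no bearing on the validity of the primary test: the primary hazard ratio uses the full analysis set under treatment policy and does not depend on this classification.

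Two stronger readings are tempting. One is that the rule hides contamination mainly in the placebo arm. Hyperkalaemia AEs may well be commoner on placebo, since Appendix E expects less good potassium control there, but the documents give no rates by arm, and the users remain visible in another table. The other is that the SAP permits prolonged binder use. It does not; it only classifies such use as rescue. The conclusion rests on the SAP's definition being applied literally. It takes no position on which clinical rule is right.

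**What to change.** Reconcile SAP 4.1.8.1 with Protocol 6.5, Table 5 and 6.5.2 before unblinding, including what counts as recurrent use. If the broader SAP definition is intended, say so and explain how it relates to the protocol's term. Then:

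1. Make rescue and disallowed non-exclusive, so that a course can count as both.
2. Tabulate as disallowed, by arm, any binder use outside the protocol's stated conditions (duration, recurrence, non-study SZC), whether or not it is AE-linked. Give participants and binder-days.
3. State whether non-study SZC given at a hyperkalaemia AE counts in the rescue endpoints.
4. Show courses with a partial or missing stop date as duration unknown. Appendix 1 would otherwise move a partial stop date to the end of the month or year and treat a missing one as ongoing. For example, a short course started on 3 March (a hypothetical date) with only the stop month, March, recorded would become 31 − 3 + 1 = 29 days and be misread as prolonged.

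The inputs are already collected: Protocol 6.5 requires reason for use and start and end dates, and 6.5.2 requires the date and time of rescue medication. The cost is one extra derivation and a disallowed count that is likely to be higher.
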